### **7.7.2 Other Restrictions and Precautions**

Participants with a condition requiring systemic treatment with either corticosteroids (>10 mg daily prednisone equivalent) or other immunosuppressive medications within 14 days of randomization are excluded. Inhaled or topical steroids, and adrenal replacement steroid doses >10 mg daily prednisone equivalent, are permitted in the absence of active autoimmune disease.

The development of serotonin syndrome has been associated with exposure to another investigational agent that inhibits the IDO1 enzyme. No case of serotonin syndrome has been observed with administration of BMS-986205. Given the possibility of a class effect, there is a theoretical risk that BMS-986205 could cause an increase in serotonin levels in the brain that might trigger serotonin syndrome when administered in combination with serotonergic agents or tryptophan supplements. Use caution and monitor for symptoms of serotonin syndrome in participants receiving concurrent serotonergic psychiatric medications and/or tryptophan supplements.

#### **7.7.2.1 Imaging Restrictions and Precautions**

It is the local imaging facility's responsibility to determine, based on participant attributes (eg, allergy history, diabetic history and renal status), the appropriate imaging modality and contrast regimen for each participant. Imaging contraindications and contrast risks should be considered in this assessment. Participants with renal insufficiency should be assessed as to whether or not they should receive contrast and if so, what type and dose of contrast is appropriate. Specific to MRI, participants with severe renal insufficiency (ie, estimated glomerular filtration rate (eGFR) < 30 mL/min/1.73 m^2) are at increased risk of nephrogenic systemic fibrosis. MRI contrast should not be given to this participant population. In addition, participants may be excluded from MRI if they have tattoos, metallic implants, pacemakers, etc.

Gentle hydration before and after IV contrast should follow local standard of care. The ultimate decision to perform MRI in an individual participant in this study rests with the site radiologist, the investigator and the standards set by the local Ethics Committee.

#### **7.7.3 Permitted Therapy**

Participants are permitted the use of topical, ocular, intra-articular, intranasal, and inhalational corticosteroids (with minimal systemic absorption). Adrenal replacement steroid doses > 10 mg daily prednisone are permitted. A brief (less than 3 weeks) course of corticosteroids for prophylaxis (eg, contrast dye allergy) or for treatment of non-autoimmune conditions (eg, delayed-type hypersensitivity reaction caused by a contact allergen) is permitted.

#### **7.7.4 Treatment of Methemoglobinemia**

The following management recommendations are intended as guidelines for the investigator and may be modified based on institutional practices or local SOC, as appropriate. See [Section 7.4.7](#) for guidance on detection of methemoglobinemia.

Initial care includes supportive measures and the administration of supplemental oxygen. In mild cases, recovery often occurs simply by delaying the administration of the offending medication. Concomitant medication lists should be reviewed for medications besides study treatment which can cause methemoglobinemia (see [Appendix 10](#)).

Further treatment is generally indicated when the methemoglobin level is above 20% or is associated with symptoms.

Intravenous methylene blue is the first-line antidotal agent and works by restoring the oxygen carrying capacity of hemoglobin by reduction of methemoglobin from its oxidized state. It is given as a 1% solution at a dose of 1 to 2 mg/kg. Most participants require only 1 dose, and symptoms should resolve within 1 hour. Methylene blue may confound the interpretation of methemoglobin levels detected by co-oximetry; alternative methods should be used after treatment with methylene blue if methemoglobin level monitoring is required. Methylene blue should be used with caution in participants with concurrent use of serotonergic psychiatric medications, as this could increase the risk of serotonin syndrome.

Exchange transfusion and hyperbaric oxygen treatment are second-line options for participants with severe methemoglobinemia whose condition does not respond to methylene blue or who cannot be treated with methylene blue. Participant transfer should occur when life-threatening methemoglobinemia that is refractory to treatment occurs in a facility that cannot provide the appropriate critical care.

### **7.7.5 Treatment of Infusion-related Reactions**

If an infusion-related reaction should occur, it might manifest with fever, chills, rigors, headache, rash, pruritus, arthralgias, hypotension, hypertension, bronchospasm, or other allergic-like reactions. All Grade 3 or 4 infusion reactions should be reported within 24 hours to the study Medical Monitor/designee and reported as an SAE if it meets the criteria. Infusion reactions should be graded according to NCI CTCAE (Version 4.03) guidelines.

Treatment recommendations are provided below and may be modified based on local treatment standards and guidelines, as appropriate:

**For Grade 1 symptoms:** (mild reaction; infusion interruption not indicated; intervention not indicated):

- Remain at bedside and monitor participant until recovery from symptoms. The following prophylactic premedications are recommended for future infusions: diphenhydramine 50 mg (or equivalent) and/or acetaminophen/paracetamol 325 to 1000 mg at least 30 minutes before additional nivolumab administrations.

**For Grade 2 symptoms:** (moderate reaction required therapy or infusion interruption but responds promptly to symptomatic treatment (eg, antihistamines, non-steroidal anti-inflammatory drugs, narcotics, corticosteroids, bronchodilators, IV fluids); prophylactic medications indicated for ≤ 24 hours):

- Stop the study treatment infusion, begin an IV infusion of normal saline, and treat the participant with diphenhydramine 50 mg IV (or equivalent) and/or acetaminophen/paracetamol 325 to 1000 mg; remain at bedside and monitor participant until resolution of symptoms. Corticosteroid and/or bronchodilator therapy may also be administered as appropriate. If the infusion is interrupted, then restart the infusion at 50% of the original infusion rate when symptoms resolve; if no further complications ensue after 30 minutes, the rate may be increased to 100% of the original infusion rate. Monitor participant closely. If symptoms recur, then no further study treatment will be administered at that visit.
- For future infusions, the following prophylactic premedications are recommended: diphenhydramine 50 mg (or equivalent) and/or acetaminophen/paracetamol 325 to 1000 mg should be administered at least 30 minutes before nivolumab infusion. If necessary, corticosteroids (up to 25 mg of hydrocortisone or equivalent) may be used.

**For Grade 3 or 4 symptoms:** (severe reaction, Grade 3: prolonged [ie, not rapidly responsive to symptomatic medication and/or brief interruption of infusion]; recurrence of symptoms following initial improvement; hospitalization indicated for other clinical sequelae (eg, renal impairment, pulmonary infiltrates). Grade 4: Life-threatening; pressor or ventilatory support indicated):

- Immediately discontinue infusion of study treatment. Begin an IV infusion of normal saline and treat the participant as follows: Recommend bronchodilators, epinephrine 0.2 to 1 mg of a 1:1000 solution for subcutaneous administration or 0.1 to 0.25 mg of a 1:10,000 solution injected slowly for IV administration, and/or diphenhydramine 50 mg IV with methylprednisolone 100 mg IV (or equivalent), as needed. Participant should be monitored until the investigator is comfortable that the symptoms will not recur. Study treatment will be permanently discontinued. Investigators should follow their institutional guidelines for the treatment of anaphylaxis. Remain at bedside and monitor participant until recovery of the symptoms.

In case of late-occurring hypersensitivity symptoms (eg, appearance of a localized or generalized pruritus within 1 week after treatment), symptomatic treatment may be given (eg, oral antihistamine or corticosteroids).

## **7.8 Treatment After the End of the Study**

Not applicable.

## **8 DISCONTINUATION CRITERIA**

### **8.1 Discontinuation from Study Treatment**

Participants **MUST** discontinue investigational product (and non-investigational product at the discretion of the investigator) for any of the following reasons:

- Participant's request to stop study treatment. Participants who request to discontinue study treatment will remain in the study and must continue to be followed for protocol specified follow-up procedures. The only exception to this is when a participant specifically withdraws

consent for any further contact with him/her or persons previously authorized by participant to provide this information.

- Any clinical AE, laboratory abnormality or intercurrent illness which, in the opinion of the investigator, indicates that continued participation in the study is not in the best interest of the participant
- Termination of the study by BMS
- Loss of ability to freely provide consent through imprisonment or involuntarily incarceration for treatment of either a psychiatric or physical (eg, infectious disease) illness. (Note: Under specific circumstances and only in countries where local regulations permit, a participant who has been imprisoned may be permitted to continue as a participant. Strict conditions apply and BMS approval is required.)
- Additional protocol-specified reasons for discontinuation (Section 8.1.1)
- Disease progression or recurrence

Refer to the Schedule of Activities (Section 2) for data to be collected at the time of treatment discontinuation and follow-up and for any further evaluations that can be completed.

In the case of pregnancy, the investigator must immediately notify the BMS Medical Monitor/designee of this event. In most cases, the study treatment will be permanently discontinued in an appropriate manner (eg, dose tapering if necessary for participant safety). Please call the BMS Medical Monitor within 24 hours of awareness of the pregnancy. If the investigator determines a possible favorable benefit/risk ratio that warrants continuation of study treatment, a discussion between the investigator and the BMS Medical Monitor/designee must occur.

All participants who discontinue study treatment should comply with protocol specified follow-up procedures as outlined in Section 2. The only exception to this requirement is when a participant withdraws consent for all study procedures including post-treatment study follow-up or loses the ability to consent freely (ie, is imprisoned or involuntarily incarcerated for the treatment of either a psychiatric or physical illness).

If study treatment is discontinued prior to the participant's completion of the study, the reason for the discontinuation must be documented in the participant's medical records and entered on the appropriate CRF page.

### **8.1.1 Discontinuation of Nivolumab**

Nivolumab treatment should be permanently discontinued for the following:

- Any Grade 2 drug-related uveitis, eye pain or blurred vision that does not respond to topical therapy and does not improve to Grade 1 severity within the time frame permitted for dose delays OR requires systemic treatment

- Any Grade 3 non-skin, drug-related AE lasting > 7 days or recurs, with the following exceptions for laboratory abnormalities, drug-related uveitis, pneumonitis, bronchospasm, neurologic toxicity, hypersensitivity reactions, infusion reactions, and endocrinopathies:
  - Grade 3 drug-related uveitis, pneumonitis, bronchospasm, neurologic toxicity, hypersensitivity reaction, or infusion reaction of any duration requires discontinuation.
  - Grade 3 drug-related endocrinopathies, adequately controlled with only physiologic hormone replacement do not require discontinuation. Adrenal insufficiency requires discontinuation regardless of control with hormone replacement.
  - Grade 3 drug-related laboratory abnormalities do not require treatment discontinuation except:
    - ◆ Grade 3 drug-related thrombocytopenia > 7 days or associated with bleeding requires discontinuation
    - ◆ Grade  $\geq$  3 drug-related AST, ALT or total bilirubin requires discontinuation\*
    - ◆ Concurrent AST or ALT > 3 x ULN and total bilirubin > 2x ULN
- \*In most cases of Grade 3 AST or ALT elevation, study treatment(s) will be permanently discontinued. If the investigator determines a possible favorable benefit/risk ratio that warrants continuation of study treatment(s), a discussion between the investigator and the BMS Medical Monitor/designee must occur.
- Any Grade 4 drug-related AE or laboratory abnormality (including but not limited to creatinine, AST, ALT, or Total Bilirubin), except for the following events which do not require discontinuation:
  - Grade 4 neutropenia  $\leq$  7 days
  - Grade 4 lymphopenia or leukopenia or asymptomatic amylase or lipase
  - Isolated Grade 4 electrolyte imbalances/abnormalities that are not associated with clinical sequelae and are corrected with supplementation/appropriate management within 3 calendar days of their onset
  - Grade 4 drug-related endocrinopathy AEs, such as, hyper- or hypothyroidism, or glucose intolerance, which resolve or are adequately controlled with physiologic hormone replacement (corticosteroids, thyroid hormones) or glucose-controlling agents, respectively, may not require discontinuation after discussion with and approval from the BMS Medical Monitor/designee.
- Any AE, laboratory abnormality, or intercurrent illness which, in the judgment of the investigator, presents a substantial clinical risk to the participant with continued nivolumab dosing
- Any event requiring 10 mg per day or greater prednisone or equivalent for more than 12 weeks
- Any event that leads to delay in dosing lasting > 10 weeks from the previous dose requires discontinuation, with the following exceptions:
  - Dosing delays to allow for prolonged steroid tapers to manage drug-related AEs are allowed. (Note: Protocol AE management algorithms provide guidance to initiate steroid

taper when AE has resolved to  $\leq$  Grade 1. Therefore, persistent Grade  $\geq$  2 AEs necessitating delay for  $>$  10 weeks would require discontinuation).

- Dosing delays lasting  $>$  10 weeks from the previous dose that occur for non-drug-related reasons may be allowed if approved by the BMS Medical Monitor/designee.

Prior to re-initiating treatment in a participant with a dosing delay lasting  $>$  10 weeks, the BMS Medical Monitor/designee must be consulted. Efficacy assessments must continue as per protocol even if dosing is delayed. Periodic study visits to assess safety and laboratory studies should also continue every 4 weeks or more frequently if clinically indicated during such dosing delays.

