### **8.1.2 Discontinuation of BMS-986205**

BMS-986205 treatment should be permanently discontinued for the following:

- Any event requiring discontinuation of nivolumab as in [Section 8.1.1](#)
- Any event requiring more than 1 dose reduction of BMS-986205 (see [Section 7.4.2](#))
- Any AE, laboratory abnormality, or intercurrent illness which, in the judgment of the investigator, presents a substantial clinical risk to the participant with continued BMS-986205 dosing
- For participants who delay BMS-986205 but continue nivolumab with or without BCG, any dose delay of BMS-986205 lasting  $>$  10 weeks will result in the discontinuation of BMS-986205 only and participants may continue treatment with nivolumab with or without BCG.
- Any occurrence of serotonin syndrome

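### Grade 4 adrenal insufficiency controlled on replacement falls under two conflicting stopping instructions: the Grade 4 endocrinopathy exception in Section 8.1.1 omits the adrenal carve-out made in Sections 7.4.5.1, 7.4.5.2 and the Grade 3 bullet

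*Combined protocol and SAP*

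**What the plan says.** Four pieces of text bear on the point.

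- **Sections 7.4.5.1 and 7.4.5.2 (criteria to resume dosing, for nivolumab and for nivolumab plus BMS-986205).** Each has a closing paragraph on drug-related endocrinopathies and ends it with the same sentence: "Adrenal insufficiency requires discontinuation regardless of control with hormone replacement". No grade is mentioned and no discretion is attached to that sentence.
- **Section 8.1.1, Grade 3 bullet.** The exception reads "Grade 3 drug-related endocrinopathies, adequately controlled with only physiologic hormone replacement do not require discontinuation", and the adrenal sentence follows at once within the same sub-bullet.
- **Section 8.1.1, Grade 4 bullet.** The exception covers "Grade 4 drug-related endocrinopathy AEs, such as, hyper- or hypothyroidism, or glucose intolerance, which resolve or are adequately controlled with physiologic hormone replacement". Its wording on control, "adequately controlled with physiologic hormone replacement (corticosteroids, thyroid hormones", opens a bracket that names corticosteroids and thyroid hormones as the replacements, and glucose-controlling agents are added after it. These events "may not require discontinuation after discussion with and approval from the BMS Medical Monitor/designee". The adrenal sentence does not appear here.
- **Sections 8.1.2 and 8.1.3.** BMS-986205 and BCG must each stop for "Any event requiring discontinuation of nivolumab as in" Section 8.1.1, so both inherit whatever rule applies to nivolumab.

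**The concern.** A stopping rule should give one answer for one event. Here the adrenal carve-out is present at Grade 3 and in both resumption sections but absent from the Grade 4 exception. A site that opens 8.1.1 at the Grade 4 bullet can reasonably conclude that continuation is open to discussion. A site that opens 7.4.5 will conclude that it is not.

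This is first a matter of participant safety and consistent conduct. Section 3.1.2 lets participants on treatment continue under Amendment 04, and lets those who had consented and were in screening be randomized, so the rule is still in use. Because 8.1.2 and 8.1.3 import it, the ambiguity covers every study drug in every arm. Safety is also the main objective left in the study, and Table 4-1 lists adverse events leading to discontinuation among the measures.

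**Working it through.** No figure is involved, so the check is a comparison of text. Take one event: a drug-related adrenal insufficiency, adequately controlled on physiologic corticosteroid replacement.

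| Provision | If Grade 3 | If Grade 4 |
|---|---|---|
| 7.4.5.1 and 7.4.5.2 | Discontinue | Discontinue |
| 8.1.1, adrenal sentence in the Grade 3 bullet | Discontinue | Discontinue if the sentence is read as ungraded; silent if it is confined to its bullet |
| 8.1.1, Grade 4 exception | Does not apply | May continue, with Medical Monitor approval |

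The Grade 3 column agrees throughout. The Grade 4 column does not.

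**Does the Grade 4 exception reach adrenal insufficiency at all?** It does not name it. Three features of the text make the reading reasonable.

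1. The examples are introduced as illustrations, so the list is open.
2. The examples are thyroid disorders and glucose intolerance. Thyroid hormones and glucose-controlling agents pair with those. Corticosteroids as a hormone replacement pair with neither, so the word points to an unlisted endocrinopathy. Sections 6.2, 7.7.2 and 7.7.3 all speak of steroids given as adrenal replacement.
3. The carve-out was written into the Grade 3 exception and not into the Grade 4 one. A reader may take the difference as deliberate.

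**Does anything visible settle the order of precedence?** Neither 7.4.5 nor 8.1.1 ranks the two instructions on this point. The clause giving Amendment 04 priority over other text does not help: its summary of key changes lists only SARS-CoV-2 criteria for 7.4.5.1 and 7.4.5.2, and only the removal of Pathology Review Committee language for 8.1. On that record neither wording is the newer instruction.

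**How far does it reach?** The event must be drug-related, Grade 4, adrenal insufficiency, and controlled on replacement. The documents report no rate of endocrinopathy for this trial, so no count can be derived. Enrollment is closed, with 135 enrolled as of early April 2021, and treatment runs for at most 52 weeks.

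**The case against.** The strongest reply is that the texts can be read together. The Grade 4 exception is general and permissive, while the adrenal sentence is specific and mandatory. Meeting the exception only means that the Grade 4 bullet does not itself force a stop. A participant whose dose was held must still satisfy 7.4.5.1 or 7.4.5.2, and both close the door on adrenal insufficiency. On that reading the outcome is the same at every grade and only a cross-reference is missing. The reading is coherent, and a careful site might adopt it. The protocol does not state it, however, and the mention of corticosteroids in the Grade 4 bullet pulls the other way.

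Other parts of the reply stand and limit the point:

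- No Grade 4 event continues automatically. Medical Monitor approval is required, and 8.1.1 separately stops treatment for substantial clinical risk in the investigator's judgment and for any event needing prednisone-equivalent doses of 10 mg per day or more for over 12 weeks. Approval does not resolve the conflict, because 7.4.5 attaches no such discretion to adrenal insufficiency.
- A reader might infer that three places state the adrenal rule without a grade limit. Only 7.4.5.1 and 7.4.5.2 clearly do; the third statement sits inside the Grade 3 sub-bullet. The related inference, that 8.1.1 treats the more severe grade more leniently, holds only if that sentence is confined to Grade 3. If it is ungraded, the tension lies within 8.1.1 itself. Either way the Grade 4 event has two instructions.
- A reader might infer that every Grade 4 endocrinopathy treated with corticosteroid replacement is affected. The documents do not support this, because the contrary instruction concerns adrenal insufficiency alone.

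**Conclusion.** The inconsistency is real and narrow. For drug-related Grade 4 adrenal insufficiency controlled on replacement, 7.4.5.1 and 7.4.5.2 require discontinuation while the Grade 4 exception in 8.1.1 allows continuation with approval, and the visible text does not choose between them. The same uncertainty passes to BMS-986205 and BCG.

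The conclusion rests on reading the open Grade 4 list as able to include adrenal insufficiency, which the text supports but does not state. It also rests on the text that can be seen: the Appendix 5 endocrinopathy algorithm is a figure not shown, so no claim is made about whether it addresses the point.

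The number of participants affected is unknown and probably small. One might infer that the safety results would be distorted through the count of adverse events leading to discontinuation. An individual event could be handled either way, but nothing in the documents shows a material effect on that count, and Section 10.3.2 plans only descriptive summaries. The reason to act is that a stopping rule still in use should be unambiguous and the correction is cheap. It should be made, but it does not call the study's design or analysis into question.

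**What to change.** Reconcile Sections 7.4.5.1, 7.4.5.2 and the Grade 3 and Grade 4 bullets of 8.1.1, so that a single adrenal-insufficiency rule appears in the same words for every grade. Which rule is intended is for the sponsor's clinical team to decide; this review takes no position. Check the endocrinopathy algorithm in Appendix 5 against the chosen wording at the same time. Sections 8.1.2 and 8.1.3 need no separate edit on this point, because they refer back to 8.1.1.

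The cost is roughly one clause, issued by administrative letter or in amendment wording, with notice to sites that still have participants on treatment. No analysis changes.
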